3.2.2 Exclusion Criteria

1) Unilateral kidney or post-renal transplantation (RRT) with preoperative AKI (KDIGO criteria) or preoperative RRT.

2) Contraindications for ta-VNS implantation include active infections, dermatitis, skin lesions, or severe psoriasis in the bilateral auricular stimulation areas; hypersensitivity to stimulator materials such as silicone or electrode gel; concurrent uncontrolled arrhythmias, symptomatic bradycardia, sick sinus syndrome, second-degree or higher atrioventricular block; existing cardiac pacemakers or defibrillators; carotid sinus hypersensitivity; uncontrolled epilepsy; or active peptic ulcers.

3) Received vagus nerve stimulation, auricular acupuncture, or transcutaneous electrical nerve stimulation treatment within 1 month prior to enrollment.

4) Drugs used long-term and unable to be safely discontinued preoperatively, which significantly affect autonomic nerve tone or renal blood flow.

5) Preoperative presence of active systemic infection or sepsis (based on Sepsis-3 criteria).

6) History of acute ischemic or hemorrhagic stroke or acute myocardial infarction within 3 months prior to enrollment.

7) Concurrent severe hepatic insufficiency (Child-Pugh class C), acute liver failure, or other serious comorbidities.

8) Vulnerable populations excluding the elderly/illiterates, including critically ill patients, psychiatric disorders, individuals with cognitive impairment, and pregnant women.

9) Other circumstances where the investigator deems the subject unsuitable for participation in the study.

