3.3 Research Content

3.3.1 Stratification, Blinding, and Intervention

After stratifying subjects according to the Cleveland Clinic scoring system for predicted dialysis-required AKI risk (high risk: ≥ 6 points vs. low-to-moderate risk: 1-5 points), independent statisticians generated computer-generated block random sequences (block size: 2 or 4) to assign participants at a 1:1 ratio to either the ta-VNS group or sham stimulation group. The grouping results were sealed in sequentially numbered opaque envelopes.

Blinding was implemented for both participants and outcome evaluators. After obtaining informed consent from participants, a non-blind study coordinator who would not be involved in subsequent clinical work publicly opened the envelope, recorded the grouping information, and handed it to a trained non-blind operator to execute the corresponding stimulation protocol. Other researchers (including those responsible for follow-up, data collection, testing, and statistical analysis) remained unaware of the grouping assignments.

The ta-VNS group received electrical stimulation via a transcutaneous auricular vagus nerve stimulator (tVNS501) applied to the left auricular cartilage. The parameters were set as follows: frequency 25Hz, pulse width 250 μ s, with a stimulation-interval cycle of 30 seconds stimulation followed by 30 seconds rest. The stimulation intensity was incrementally increased starting from 0.4V in 0.4V increments until the subject experienced pain, then adjusted downward to just below the pain threshold to determine the optimal stimulation intensity. The stimulation coverage spanned preoperative, intraoperative, and postoperative phases: beginning on the day of surgery upon entering the preoperative preparation room and continuing until the patient was transferred to the ICU, followed by 6 hours of stimulation. From postoperative days 1 to 5, the stimulation regimen was restored to twice daily (at 9:00 AM and 2:00 PM) with each session lasting 120 minutes [42-44].

In the sham-stimulation group, electrodes were placed at the same site and within the same cycle period with optimal intensity determined, but stimulation output was turned off without administering actual electrical stimulation.

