All equipment was dedicated to specific individuals and labeled for identification. Participants were informed that the stimulation process might induce or fail to induce any discomfort. Heart rate and blood pressure were continuously monitored during the intervention. If persistent heart rate <50 beats per minute, significant hemodynamic instability, or other severe adverse events occurred, stimulation was immediately discontinued and recorded.

The tympanic vagus nerve stimulator (tVNS501) involved in this study exhibits off-label use (off-label indication). The tympanic vagus nerve stimulator (tVNS501) (as specified in the package insert) may be used as adjunctive therapy for sleep disorders, fatigue, anorexia, and anxiety symptoms; when combined with medications, it is applicable for adjunctive treatment of diabetes mellitus. In this study, the tympanic vagus nerve stimulator (tVNS501) was employed to prevent AKI following cardiac surgery under CPB, constituting off-label use. Only the left ear unit was utilized in this study, as the device's built-in metal electrodes enable precise stimulation of the cochlear cone. Although the right ear unit was available, it lacked stimulation functionality and was neither worn nor activated during the study.

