the Confusion Assessment Measure (CAM) or the ICU Confusion Assessment Measure (CAM-ICU) for both preoperative and postoperative periods (over 7 consecutive days). Early cognitive function was screened using the Mini-Mental State Examination (MMSE) on preoperative day 1, postoperative day 3, and postoperative day 7. Sleep quality was evaluated using the Richards-Campbell Sleep Questionnaire (RCSQ) on preoperative day 1, postoperative day 1 morning, and postoperative day 3 morning to assess prior night sleep status. Recovery quality was scored using the 15-item Quality of Recovery Scale (QoR-15) on preoperative day 1, postoperative day 1, postoperative day 3, and postoperative day 7. Pain and analgesic demand were recorded as baseline pain levels on preoperative day 1 and pain numerical scores (NRS) within 48 hours postoperatively (recorded at least once daily), along with total opioid consumption within 48 hours postoperatively (converted to oral morphine equivalents).

7) Perioperative complications and mortality rate

The incidence rates of cardiovascular complications (including new-onset atrial fibrillation and other arrhythmias, acute myocardial infarction, postoperative myocardial injury, and low cardiac output syndrome), stroke, pulmonary embolism, pulmonary infection, deep vein thrombosis, surgical site deep infection, and all-cause mortality within 30 days postoperatively.

8) Resource consumption

Length of hospital stay, ICU stay duration, and re-admission rate due to complications.

9) Biomarkers

To comprehensively evaluate patient status and explore the pathogenesis of AKI, this study detected the following biomarkers:

a) Routine testing: Collect daily routine laboratory data before surgery and for 7 days postoperatively, including C-reactive protein (CRP), neutrophil-to-lymphocyte ratio (NLR), cardiac troponin (cTn), creatine kinase isoenzyme MB (CK-MB), N-terminal pro-brain natriuretic peptide (NT-proBNP), and serum cystatin C.

b) Specific inflammatory markers and renal injury indicators: Peripheral blood samples were collected at 24h, 48h, and 72h postoperatively and placed in EDTA anticoagulation tubes. Plasma interleukin-6 (IL-6) and neutrophil gelatinase-associated lipocalin (NGAL) concentrations were detected in batches using the ELISA method.

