The proportion of patients requiring RRT during hospitalization was compared between groups using χ^2 test or Fisher's exact probability method; the duration of RRT was compared between groups based on its distribution characteristics using independent samples t-test or Mann-Whitney U test.

The proportion of patients with persistent AKI was compared between groups using the χ^2 test; the time to renal function recovery was plotted as cumulative recovery curves using the Kaplan-Meier method, with intergroup comparisons performed via the log-rank test. Patients who did not recover during the observation period were treated as censored data.

Serum creatinine and eGFR at 30 days postoperatively were compared between groups using independent samples t-test or Mann-Whitney U test based on their distribution characteristics.

HRV was analyzed using generalized estimating equations, with grouping, time points, and their interaction terms included as fixed effects. The optimal working-related matrix structure was selected based on the quasi-likelihood independence criterion. Significant group \times time interaction terms indicated statistically distinct temporal trends in HRV metrics between the two groups.

The duration of mechanical ventilation, peak/mean values of vasoactive drug index, peak/mean values of postoperative 48-hour pain NRS scores, and total opioid consumption were compared between groups using independent samples t-test or Mann-Whitney U test based on

their distribution characteristics. The incidence of delirium was compared between groups using χ^2 test. MMSE, QoR-15, and RCSQ were analyzed using generalized estimating equations (GEE), with model specifications identical to those used for HRV analysis.

The incidence rates of new-onset atrial fibrillation, pulmonary infection, stroke, and 30-day all-cause mortality were compared between groups using χ^2 test or Fisher's exact probability method. If the number of events was sufficient, Cox proportional hazards regression model could be employed for analysis, with adjustment for covariates when necessary. Hazard ratios (HR) and their 95% CI were reported.

Hospitalization duration and ICU stay duration were treated as continuous variables, which were expected to follow a skewed distribution. Between-group comparisons were performed using the Mann-Whitney U test. The re-admission rate due to complications was compared using the χ^2 test.

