GEE were employed to analyze differences in the temporal variation trajectories of routine laboratory parameters and plasma IL-6/NGAL levels between two groups. The model included grouping, time, and their interaction as fixed effects, with subjects as random effects. Appropriate work-related matrices and distribution families were selected to assess the significance of the group \times time interaction. Independent samples t-test or Mann-Whitney U test was used to compare postoperative monocyte α 7nAChR expression levels, intracellular IL-6+ proportion, and Th17/Treg ratio at various time points between the two groups. GEE analysis was also conducted to evaluate overall trends and intergroup differences. Spearman correlation analysis was employed to investigate associations between immune cell markers (α 7nAChR, IL-6+, Th17/Treg), plasma biomarkers (IL-6, NGAL), and clinical outcomes (AKI incidence rate, peak serum creatinine level).

[figure not shown]
To determine the minimum number of stimulation days required to achieve clinical efficacy, the completion of stimulation was defined as when the actual daily stimulation duration reached $\geq 80\%$ of the planned duration. Based on the total number of days (0-6 days) during which subjects completed stimulation, a multivariate logistic regression analysis was performed to examine the dose-response relationship between cumulative stimulation days and the incidence of AKI, thereby identifying the critical number of days when the protective effect tends to plateau.

Subgroup analysis was conducted based on the following prespecified factors: gender, left ventricular ejection fraction (<35% vs. $\geq 35\%$), age (<65 years vs. ≥ 65 years), preoperative eGFR (<90 vs. ≥ 90 mL/min/1.73 m²), CPB duration (<120 min vs. ≥ 120 min), and surgical type (high-risk group [valve and coronary artery combined/aortic surgery] vs. low-to-moderate risk group [valve and septal repair]). Subgroup analysis was implemented in single-factor logistic regression models by introducing interaction terms between grouping and subgroup variables, with OR values and 95% CI for each subgroup visually presented in forest plots.

Safety analysis was based on the safety dataset (all subjects who received at least one stimulation). The incidence rates of all adverse events and serious adverse events were compared between groups using the χ^2 test or Fisher's exact probability method.

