3.4 Research Flowchart

IV. Sample Size Calculation

The sample size for this study was estimated based on preliminary experimental results from our research center. In the pilot study, the incidence rates of CPB-associated AKI in the ta-VNS group and sham stimulation group were 17.1% and 37.9%, respectively. With a significance level of $\alpha = 0.05$ (bilateral) and a power of $1 - \beta = 0.80$, calculated using G*Power software (version 3.1.9.7), 68 patients were required in each group. Considering a 10% dropout rate, a total of 152 patients were enrolled in this study, with 76 patients in each group.

V. Data Management and Confidentiality

Only investigators authorized by the principal investigator are permitted to access or analyze data. Computer systems used for data management must be password-protected, and paper documentation must be locked.

All information related to the subject's identity is kept confidential, and such information shall not be disclosed beyond the scope permitted by applicable laws and/or regulations.

VI. Informed Consent

Prior to enrollment in this study, the investigator responsible for obtaining informed consent must provide each participant with a comprehensive written explanation regarding the study's objectives, nature, procedures, potential benefits, and risks. Participants should be informed of their right to withdraw from the study at any time. Before enrollment, each participant must be fully informed and given sufficient time to consider participation. Enrollment is permitted only after voluntary participation and signing of the informed consent form.

The vulnerable groups potentially involved in this study include elderly individuals and illiterate persons. If the subject is unable to read or sign the informed consent form due to lack of capacity for action, their guardian must act as proxy for the informed consent process and sign the document. If the subject lacks the ability to read the informed consent form (e.g., illiteracy), a witness must observe the informed consent process and sign the consent form.

VII. Adverse Events and Related Management Measures

ta-VNS is a selective, non-invasive, and low-risk effective VNS strategy. The primary

adverse events include pain, influenza-like symptoms, and local skin discomfort, which resolve immediately after cessation of stimulation. To date, no literature has reported serious adverse events associated with this procedure.

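### The safety analysis compares only total adverse and serious adverse events, not the bradycardia, instability and stimulation stops the plan guards against, so a real excess could be diluted

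*Combined protocol and SAP*

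**What the plan says.** Three parts of the document treat cardiac slowing and unstable circulation as risks of stimulation.

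- Section 3.2.2 lists as contraindications, among others, "symptomatic bradycardia, sick sinus syndrome, second-degree or higher atrioventricular block".
- Section 3.3.1 requires continuous heart rate and blood pressure monitoring and adds: "If persistent heart rate <50 beats per minute, significant hemodynamic instability, or other severe adverse events occurred, stimulation was immediately discontinued and recorded". The word before the last item places the first two among adverse events.
- Section 3.3.2.2, item 7, collects cardiovascular complications: "new-onset atrial fibrillation and other arrhythmias, acute myocardial infarction, postoperative myocardial injury, and low cardiac output syndrome".

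The analysis in section 3.3.3 does not follow these through. For complications it states: "The incidence rates of new-onset atrial fibrillation, pulmonary infection, stroke, and 30-day all-cause mortality were compared between groups". For safety it takes patients with at least one stimulation and says: "The incidence rates of all adverse events and serious adverse events were compared between groups", by chi-square or Fisher test. No section names a comparison by arm of persistent slow heart rate, of hemodynamic instability, or of stimulation stopped under the rule.

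Section VII says that the main "adverse events include pain, influenza-like symptoms, and local skin discomfort". It mentions neither slow heart rate nor instability. Nothing states whether AKI or the listed complications count as adverse events.

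**The concern.** Safety is a stated objective alongside efficacy (section 3.1), and section 3.3.1 says the device is used off-label. A reader will want to know whether stimulation slowed the heart or destabilised the circulation more often than sham. The plan records the stops that bear on this, but its stated safety result is two totals. An all-adverse-event rate counts a patient once, whatever the event. A patient who has bradycardia and also some unrelated event adds nothing to the contrast between arms. The more common unrelated events are, the less of the excess remains visible. The trial could then report similar adverse event rates although the specific harm was several times more frequent under stimulation.

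**Working it through.** **Inputs from the plan (section IV).** 76 patients per arm, and AKI in 37.9% (sham) and 17.1% (ta-VNS). The arm size reproduces closely: the unpooled normal formula gives (1.960 + 0.842)² × (0.171×0.829 + 0.379×0.621) / 0.208² = 68.4, so 69 against the stated 68, and 68 / 0.90 = 75.6, so 76. The plan states no rate for bradycardia, instability, stops, all adverse events or serious adverse events, so there is no safety figure to reproduce.

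**Assumptions.** Stops for slow heart rate or instability occur in b = 2% of sham and 12% of ta-VNS patients. A share q of each arm has some other adverse event, equal between arms and independent of b. All 76 per arm are in the safety set.

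**Formulas.** Any-event rate = 1 − (1 − q)(1 − b). Difference between arms = (1 − q)(0.12 − 0.02). Power is by exact enumeration of two binomials with a two-sided 5% test (chi-square, or Fisher when an expected count is below 5), counting only results that show an excess with ta-VNS.

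| Comparison | Sham | ta-VNS | Difference (points) | Power |
|---|---|---|---|---|
| Specific event, direct | 2.0% | 12.0% | 10.0 | 68% |
| Any event, q = 10% | 11.8% | 20.8% | 9.0 | 33% |
| Any event, q = 20% | 21.6% | 29.6% | 8.0 | 20% |
| Any event, q = 40% | 41.2% | 47.2% | 6.0 | 11% |
| Any event, q = 60% | 60.8% | 64.8% | 4.0 | 8% |
| Any event, q = 80% | 80.4% | 82.4% | 2.0 | 5% |

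**Other effect sizes.** At 2% vs 20%, power is 98% directly and 72%, 50%, 26%, 15% and 9% in the total at q = 10%, 20%, 40%, 60% and 80%. At 2% vs 6%, even the direct comparison has only 12%.

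**What an interval would show** (half-width = 1.96 × √[p₁(1−p₁)/76 + p₀(1−p₀)/76]). Direct, 12% vs 2%: 1.96 × √(0.00139 + 0.00026) = 8.0 points, so 10 points (about 2 to 18). In the total at q = 60%: 1.96 × √(0.00300 + 0.00314) = 15.4 points, so 4 points (about −11 to 19).

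**If AKI were counted as an adverse event** (not stated in the documents). At q = 60%, sham is 1 − 0.40×0.98×0.621 = 75.7% and ta-VNS is 1 − 0.40×0.88×0.829 = 70.8%. The total then favours ta-VNS by about 5 points, and the chance of a significant excess with ta-VNS is 0.4%.

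**If titration pain were counted** (also not stated). Output is raised "until the subject experienced pain", and sham patients also have their optimal intensity determined. Both arms would then be near 100%, and the total would carry no information.

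**The case against.** A reader might infer that the adverse event total would reverse the harm, because it includes AKI, or that it would certainly hide it. The documents support neither. AKI is the primary outcome, the complications are secondary outcomes, and the only adverse events that section VII names are pain, influenza-like symptoms and skin discomfort. Without AKI or a similar outcome in the total, and with other events equal between arms, the expected difference keeps its direction and only shrinks. How much it shrinks depends on a background rate that the plan does not give. Nor does any section say that pain evoked during titration is recorded as an adverse event.

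It would also be too strong to say that nothing related is compared. Section 3.3.3 has a default chi-square or Fisher rule for categorical variables, which can be applied to other arrhythmias and low cardiac output syndrome even though the complications sentence does not name them. The vasoactive drug index is explicitly compared by arm. These are partial substitutes. The arrhythmia category mixes slow and fast rhythms. The drug index measures postoperative drug use, so it counts neither bradycardia nor stops and misses intraoperative stimulation.

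Serious adverse events are compared separately, and some of these events could qualify. That comparison is not modelled here: the documents do not define serious, and an event severe enough to stop stimulation need not be serious.

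Finally, a direct comparison has its own limits. It would usually miss a three-fold excess. The operator is not blinded, so the decision to stop may differ by arm. Low heart rate during bypass may reflect the procedure in both arms. These points stand, and they argue for descriptive reading rather than against reporting the events.

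**Conclusion.** The concern holds as a risk of dilution. The plan treats slow heart rate and instability as harms to guard against, records stops for them, and specifies no direct comparison of either. Under the assumed 2% vs 12%, power falls by about half at a 10% background (68% to 33%) and to 5–11% at 40–80%. All of these event rates are assumptions, other events are taken as independent and equal between arms, and the figures concern the all-adverse-event total only. A result favouring ta-VNS, or a total near 100% in both arms, depends on counting AKI (or another outcome that ta-VNS lowers) or titration pain. The plan's silence on these leaves the meaning of the total undefined. The main gain from a named comparison is an interpretable estimate with an interval, not assured detection. The change should be made before the analysis, but it does not affect the primary result.

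**What to change.** In the safety paragraph of section 3.3.3:

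- Add, for each arm, the number of patients whose stimulation was stopped under the section 3.3.1 rule, by recorded reason (persistent heart rate below 50, hemodynamic instability, other severe adverse event), with risk difference and 95% CI, to be read descriptively. State how a sham session that meets the rule is counted, since its output is already off.
- Tabulate intraoperative and postoperative stops separately where timing is recorded. Note that the operator is unblinded and that low heart rate during bypass may arise from the procedure in either arm.
- Report adverse events by type. Keep AKI, the other efficacy outcomes and pain evoked in titration out of the all-adverse-event rate, and say so.

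In the complications paragraph of the same section, name every complication listed in section 3.3.2.2, item 7, and split other arrhythmias into slow and fast.

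No stopping threshold or other clinical rule is changed. The cost is SAP wording and a few tables, with no added patients or visits. The case report form must capture the reason and time of each stop and the type of arrhythmia, because section 3.3.1 says only that a stop is recorded. The downside is a few more unadjusted safety comparisons with low power.

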through a meticulously designed randomized controlled clinical trial. The goal is to develop an innovative neuromodulation strategy for perioperative renal protection.

II. Research Objective

This study aims to evaluate the efficacy of perioperative transcutaneous auricular vagus nerve stimulation (ta-VNS) in reducing the incidence of postoperative acute kidney injury (AKI) in patients undergoing elective cardiopulmonary bypass surgery through a randomized controlled trial. The hypothesis posits that perioperative ta-VNS application significantly lowers the AKI incidence rate within 7 days postoperatively compared to sham stimulation. Additionally, this study will investigate the effects of ta-VNS on AKI severity, related renal function parameters, and biomarkers to validate its clinical value as a non-invasive neuromodulation approach for perioperative renal protection.

III. Research Design and Methods

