c) Peripheral blood immune cell phenotype analysis: Peripheral blood samples were collected at 24h, 48h, and 72h postoperatively and placed in EDTA anticoagulation tubes. Peripheral blood mononuclear cells (PBMCs) were isolated within 4 hours. Multicolor flow cytometry was employed to detect the expression level of $\alpha 7$ nAChR on the surface of CD14⁺ monocytes and the proportion of intracellular IL-6⁺, as well as the proportions of Th17 (IL-17A⁺) and Treg (CD25⁺CD127^{low/-}) subsets among CD4⁺ T cells, with the Th17/Treg ratio calculated. The analysis was performed using a CytoFLEX flow cytometer and FlowJo software.

Note: Items b and c represent exploratory additional testing mechanisms. A total of 40 patients were selected from the overall sample using stratified random sampling for additional diagnostic evaluation items. The stratification factors included group assignment and Cleveland Clinic score-predicted risk level of dialysis-dependent AKI.

All samples were processed and analyzed using a blinded method. All blood samples were aliquoted into low adsorption cryovials (0.5 mL/vial) to avoid repeated freeze-thaw cycles, and immediately stored in an ultra-low temperature freezer at -80 ° C. Complete sample numbering and time records were established. Upon study completion, the samples were disposed of in accordance with medical waste disposal standards.

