3.3.3 Statistical Analysis Plan

All data in this study were processed using SPSS 26.0 and R 4.3.0 software.

For continuous variables, the Shapiro-Wilk normality test is first performed. Variables conforming to normal distribution are expressed as "mean \pm standard deviation," with intergroup comparisons conducted using the independent samples t-test. Variables not conforming to normal distribution are represented by median values (25th and 75th percentiles), and intergroup comparisons are performed using the Mann-Whitney U rank-sum test. Categorical variables are presented as frequencies (percentages), with intergroup comparisons analyzed using the χ^2 test. If theoretical frequencies do not meet the test requirements, the Fisher exact probability method must be employed.

The primary endpoint of this study was the incidence of AKI within 7 days postoperatively, analyzed based on the intention-to-treat principle. Kaplan-Meier curves were constructed to plot the cumulative incidence of AKI within 7 days postoperatively for both groups, with intergroup comparisons performed using the log-rank test. The Cox proportional hazards regression model was employed to estimate the hazard ratio (HR) and its 95% confidence interval for the ta-VNS group versus the sham stimulation group. A single-factor COX regression model incorporating only grouping variables was first fitted to estimate the crude effect, followed by a multivariate

COX regression model that adjusted for preoperative eGFR (<90 vs. ≥ 90 mL/min/1.73 m²), diabetes history (present vs. absent), left ventricular ejection fraction (<35% vs. $\geq 35\%$), and surgical type (high-risk group [valve and coronary artery combined/aortic surgery] vs. low-risk group [valve and septal repair]) as covariates. Under the random missingness assumption, imputation models were constructed based on covariates related to outcomes and missingness states, generating 20 imputed datasets for analysis, with results combined according to the Rubin rule. Under the non-random missingness assumption (all missing values in the ta-VNS group were AKI, while all missing values in the sham stimulation group were non-AKI), intergroup comparisons were re-evaluated.

The severity of AKI was analyzed using multivariate ordered logistic regression, adjusting for the same covariates as in the primary analysis and testing the proportional hazards assumption. Results were reported as odds ratios (OR) and their 95% confidence intervals (CI).

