Unless otherwise specified, all tests were conducted as two-tailed tests with a significance level set at $\alpha = 0.05$, meaning that differences were considered statistically significant when $P < 0.05$.

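### At least 31 secondary tests and 6 subgroup interaction tests share an unadjusted P<0.05 significance rule, with no ranking, multiplicity control or exploratory label

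*Combined protocol and SAP*

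**What the plan says.** Section 3.3.3 names a single primary endpoint: "The primary endpoint of this study was the incidence of AKI within 7 days postoperatively". It then sets out between-group tests for nine groups of secondary outcomes, starting with AKI severity ("The severity of AKI was analyzed using multivariate ordered logistic regression"), and does not rank them. Significant group-by-time terms are given an inferential reading; for heart rate variability, such "interaction terms indicated statistically distinct temporal trends in HRV metrics between the two groups".

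Six subgroup factors follow ("Subgroup analysis was conducted based on the following prespecified factors"), each fitted with an interaction term. The section ends with the general rule: "all tests were conducted as two-tailed tests with a significance level set at" 0.05, so that "differences were considered statistically significant when" P is below 0.05.

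The only exploratory label on any secondary outcome is in the note under Biomarkers in section 3.3.2.2: "Items b and c represent exploratory additional testing mechanisms". It applies to the 40-patient substudy. Section II says that effects on AKI severity, related renal function parameters and biomarkers will be studied "to validate its clinical value as a non-invasive neuromodulation approach for perioperative renal protection".

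**The concern.** The plan contains no gatekeeping on the primary result, no order among the secondary outcomes and no adjustment for their number. Two items are labelled exploratory, so a reader will take the rest as not exploratory. For severity, renal function and biomarkers, the word *validate* in section II strengthens that reading.

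What is at stake is how the results may be described. A report that follows the plan to the letter could call any secondary outcome or subgroup interaction statistically significant at P<0.05. It would give no indication that several dozen such comparisons were made, or that one or two false positives among them are to be expected when the treatment does nothing.

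**Working it through.** **Plan's own figure.** The documents state no family-wise error rate, so there is none to reproduce. The sample size in section IV rests on the primary endpoint alone: 68 per group, and 68 / 0.90 = 75.6, rounded up to 76 per group and 152 in total. It is not affected by this point.

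**Count of tests named in section 3.3.3, without biomarker items b and c.**

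| Outcome group | Tests |
|---|---|
| AKI severity | 1 |
| RRT: proportion, duration | 2 |
| Persistent AKI, recovery time | 2 |
| Day-30 creatinine, eGFR | 2 |
| HRV (counted once; metrics are not named) | 1 |
| Early recovery: ventilation time; vasoactive index peak and mean; pain peak and mean; opioid total; delirium; MMSE; QoR-15; RCSQ | 10 |
| New atrial fibrillation, pulmonary infection, stroke, 30-day death | 4 |
| Hospital stay, ICU stay, re-admission | 3 |
| CRP, NLR, cTn, CK-MB, NT-proBNP, cystatin C trajectories | 6 |
| **Total** | **31** |

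The subgroup interactions (gender, LVEF, age, eGFR, CPB duration, surgical type) add 6, giving 37.

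The 31 is a floor. HRV has more than one metric. Section 3.3.2.2 also lists seven complications that section 3.3.3 does not name but that fall under its general rule for categorical variables. Adding those seven gives 38.

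The outcomes covered by the section II sentence are severity (1), RRT (2), persistent AKI and recovery (2), day-30 function (2) and routine markers (6): 1 + 2 + 2 + 2 + 6 = 13.

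**Formulas, assuming no treatment effect on any outcome.**

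- Expected false positives: 31 × 0.05 = 1.55; for 37 tests, 37 × 0.05 = 1.85.
- At least one P<0.05 in either direction, independent tests: 1 − 0.95^m. For m = 31 this is 0.796; m = 37, 0.850; m = 38, 0.858; m = 13, 0.487; m = 6, 0.265.
- At least one favouring ta-VNS, every test treated as directional, independent: 1 − 0.975^m. For m = 31 this is 0.544; m = 13, 0.280.

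**Correlated tests.** The documents give no correlations, so a common correlation is an assumption, shown as a range. Test statistics were simulated as equicorrelated normal variables (400,000 draws per setting) and counted when |z| > 1.96, or when z > 1.96 for the favourable direction.

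| Set of tests | Direction | Independent | Correlation 0.5 | Correlation 0.8 |
|---|---|---|---|---|
| 31 secondaries | either | 80% | 51% | 26% |
| 31 secondaries | favours ta-VNS | 54% | 26% | 13% |
| 13 section II tests | either | 49% | 33% | 19% |
| 13 section II tests | favours ta-VNS | 28% | 17% | 10% |
| 6 interactions | either | 26% | 21% | 14% |

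**Sparse outcomes.** Fisher's exact test on rare events runs well below its nominal level: about 0.002 at a 2% event rate with 76 per arm. Dropping RRT proportion, RRT duration, stroke and death leaves 27 tests. The either-direction figures are then 75% if independent and 48% at correlation 0.5.

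**The case against.** The strongest reply is that a reader might infer that a chance success for ta-VNS is more likely than not. The figures do not support that. The 80% and 51% count results in either direction, including those favouring sham. With every test treated as directional, a favourable chance result exceeds one half only near independence: 54% at zero correlation, 47% at 0.1 and 41% at 0.2. Independence is implausible for creatinine with eGFR, peak with mean, or ICU with hospital stay. This part of the reply stands, with one qualification. Ten of the 31 are group-by-time tests, for which the plan states no favourable direction. Counting those ten either way and the other 21 only when favourable gives 65% if independent, 52% at correlation 0.3 and 40% at 0.5. Whether the figure passes one half therefore depends on a correlation that the documents do not give.

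Other parts also stand:

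- The *validate* wording in section II covers about 13 tests, not every secondary outcome and no subgroup. The hypothesis stated there concerns AKI incidence alone, and section 3.3.2.2 describes the biomarkers partly as a way of exploring pathogenesis.
- A reader might infer that a significant secondary outcome could rescue a failed primary comparison. No passage says so; the plan is only silent on gatekeeping.
- A reader might infer that the 5% level is void for the secondary outcomes. It holds for each test singly, and no family-wise rate is promised.
- The subgroup plan already tests interactions and shows odds ratios with 95% confidence intervals in forest plots. What it lacks is a label.

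None of this removes the blanket rule or supplies a ranking.

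**Conclusion.** The point holds as one about unadjusted multiple testing and labelling. One sentence in section 3.3.3 makes P<0.05 the criterion of significance for at least 31 secondary and 6 interaction tests, without hierarchy, multiplicity control or exploratory label. With no treatment effect, one or more either-direction false positives among the 31 would occur with a chance of 26% to 80% over assumed correlations of 0.8 down to 0. The favourable-direction range is 13% to 54% if all tests are directional. Even the low ends exceed twice 0.05.

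The counts are read directly from the plan. The probabilities rest on a common correlation chosen for illustration and on each test holding its nominal level, which sparse outcomes will not reach. The number of secondary tests does not affect the primary endpoint's type I error. This should be changed before unblinding, but it does not threaten the primary comparison.

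**What to change.** In section 3.3.3, limit the P<0.05 significance claim to the primary endpoint. If the sponsor wants confirmatory secondary outcomes, add a short prespecified fixed sequence of its own choosing. The first is tested at two-sided 0.05 only if the primary is significant, and each later one only if all earlier steps are significant. Label all other secondary outcomes and all six subgroup interactions exploratory, and report them as estimates with 95% confidence intervals without calling them statistically significant. In section II, change *to validate* to *to explore* for outcomes outside that sequence.

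If a sequence is chosen, endpoints should keep their present definitions. For example, moving persistent AKI from patients with AKI to all randomised patients would redefine an endpoint in section 3.3.2.2, which is more than a wording change.

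The cost is wording in two sections: no extra patients, no extra data and no loss of power for the primary endpoint. The downside is that outcomes outside the sequence can no longer be claimed as statistically significant. The alternative of a Bonferroni rule would need P below 0.05 / 31 = 0.0016 for the secondary outcomes, or 0.05 / 37 = 0.00135 with the interactions included.
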